4.6.4 Removal of Device	17
4.7 Examination Requirements	18
4.8 Enrollment, Randomization, Masking and Unmasking	20
5 Safety Monitoring and Reporting	22
5.1 Safety Monitoring Committee	22
5.2 Adverse Experience Reporting	22
5.3 Obligations of Site Investigators	22
5.4 Obligations of Study Sponsor	25
5.5 Adverse Events Defined	25

5.6	Withdrawal Criteria	27
6	Statistical Considerations	28
6.1	Description of Trial	28
6.2	Analysis Populations	28
6.3	Efficacy and Safety Variables	28
6.4	Sample Size Rationale	29
6.5	Statistical Analysis Plan	29
6.6	Interim Monitoring	29
7	Human Participant Protection	29
8	Study Risk and Precautions	31
8.1	NT-501 Device Implant and Sham Surgery	31
8.2	CNTF and CNTF Producing Cells	31
8.3	Dilation and Anesthetic Drops	31
8.4	IOP Examination and ERG	31
9	Confidentiality and Access to Source Documents and Data	31
10	Summary of GCP Compliance	32
10.1	Investigator Responsibilities	32
	Institutional Review Board	33
	Review of Protocol, Consent and Recruitment Materials	33
10.2	Data Handling and Record Keeping	34
10.3	Protocol Amendments	34
10.4	Monitoring Plan	35
10.5	Retention of Records	36
11	Certifications and Training Requirements	36
11.1	Certification for AOSLO Image Acquisition and Analysis	36
11.2	Certification for Humphrey Visual Field Testing	38
11.3	Professional Licensure	38
12	References	39
13	Appendix: NT-501 Implant Accessories: Surgical Tool Information	43

Protocol Summary

Protocol Title:	Photoreceptor Structure in a Phase 2 Study of Encapsulated Human NTC-201 Cell Implants Releasing Ciliary Neurotrophic Factor (CNTF) for Participants with Retinitis Pigmentosa Using Rates of Change in Cone Spacing and Density as the Primary Outcome
Protocol Designation:	CNTF/UCSF
Test Article:	NT-501 Encapsulated cell intraocular implant; releasing CNTF.
Primary Endpoint(s):	The primary efficacy variable is the rate of change in cone spacing and cone density from baseline to 30 months.

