2.3 Rationale for Use of Sham Surgery

This Phase 2 study will explore the effect on cone spacing and cone density over a 24-month period of CNTF release by the NT-501 intravitreal device to establish whether CNTF delivered in this manner can improve cone photoreceptor survival or lessen the decline in cone density relative to the contralateral control eye. Measures of change in visual acuity, visual field sensitivity and disease modification will be collected over a total of 24 months as secondary

outcomes. Given this observation period to reach the primary outcome and the relatively small, absolute magnitude of improvement expected, a control sham treatment with minimal risk to the fellow eye is justified to qualify the chance that any observed differences are a result of a participant effort rather than from the treatment itself.

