- Assuming a recommendation to continue enrollment results from the SMC's review of safety data (up to one month post implant), the second patient will undergo surgical implantation of the investigational product during day's 1 – 5 of week 5.
- The 2-month post implant safety data for patients 1 and the one-month post-implant safety data for patient 2 will be supplied to the chairman of the SMC at the beginning of week 9.

The SMC's recommendation was to continue enrollment following the SMC review of safety data (up to two month post implant). The remaining patients will undergo surgical implantation of the investigational product in accordance with enrollment.

Devices will not be explanted except in instances where it is medically advised due to an adverse event. An examination for safety will occur one day following surgical implant and periodically thereafter.

All participants will be followed clinically for 30 months.

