4.1 Outcomes

Primary Outcome:

The primary outcome is rate of change in cone spacing and rate of change in cone density as determined using AOSLO images of regions of interest (ROIs) preselected at baseline in eyes treated with CNTF compared to contralateral eyes treated with sham surgery over 30 months. Cone spacing and density will be measured by 3 independent graders who will remain fully masked to the treatment assignment throughout the duration of the trial. We will compare rates of change in cone spacing and cone density between CNTF-treated and contralateral sham-treated eyes through 30-months using pooled linear regression.

Secondary Outcomes:

Secondary outcome measures will involve comparing rates of change in standardized measures of visual function between CNTF- and sham-treated eyes. Secondary outcomes will include the following functional and structural assessments: mean and median change in best spectacle-corrected visual acuity (BCVA) using the ETDRS protocol, changes in visual field sensitivity and foveal sensitivity in decibels (dB) using automated static perimetry using the Humphrey visual field 10-2 protocol and rod and cone-mediated fundus-guided microperimetry using a modified Nidek MP1, changes in thickness of the outer nuclear layer (ONL) and outer segment plus RPE (OS+) layer thickness as measured using spectral-domain optical coherence tomography (SD-OCT), and changes in full-field ERG scotopic and photopic standard a- and b-wave amplitudes and timing from baseline to 36 months. All parameters except full-field ERG will be measured at 6, 12, 18, 24, 30 and 36 months after implant surgery; standard full-field ERG will be performed according to ISCEV standards at baseline, 12, and 24 months.

Safety Outcomes:

Safety of the NT-501 ECT technology implant has been demonstrated in prior Phase 1 and Phase 2 trials of the implant. Separately from efficacy outcomes which demonstrate a reduction or increase in function, safety parameters will continue to be collected and assessed by the following outcomes (occurrence of these outcomes does not necessarily require explant):

- Rejection or extrusion of the NT-501 device.
- Protocol-related abnormal findings from serum chemistry, hematology, and urinalysis (those abnormal findings that are determined to be clinically significant by the Principal Investigator).

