6.3 Efficacy and Safety Variables

The primary efficacy variable is the rate of change in cone spacing and cone density from baseline to 24 months. Secondary efficacy variables will include: mean change from baseline value in Humphrey Visual Field Sensitivity (VFS) from baseline to 24 months, mean change in “5-point” VFS from baseline to month 24 (using the 5 retinal points with greatest average change), mean change from baseline in Best Corrected Visual Acuity (BCVA) at 12, 18, and 24 months, and changes in ERG, Optical Coherence Tomography (OCT), clinical grades of

inflammation (anterior chamber cell and vitreous haze grades), and vision-related quality of life (NEI-VFQ25) at each visit.

The mean change in VFS will be calculated using the sum of all points at baseline and each follow-up visit. Likewise, the 5 points with greatest change from baseline will be selected for each patient based on the average score per point across replicates at baseline and at month 24; the mean of these 5 points will be used to compute the change from baseline in “5-point” VFS.

Safety variables will include the incidence of adverse events, changes in vital signs, marked changes in clinical laboratory data, ECG abnormalities, and findings during physical examinations.

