6.4 Sample Size Rationale

The primary analysis will compare the mean rate of change in cone spacing and cone density between CNTF-treated and control eyes over the 24-month study period using pooled linear regression. With a minimum 10 patients the sample size will provide in excess of 80% power to detect a difference of 0.084 arcminutes in cone spacing (twice the effect reported per year in preliminary studies (Talcott et al, 2010), assuming a within-region standard deviation of 0.11 (based on preliminary data, and using a paired-subjects t-test as a basis for power calculations).

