7.5.1.1 Primary analysis

While we consider both cone spacing and density to be primary outcome measures, for the purpose of formal hypothesis testing for the efficacy aims of the trial, we chose the outcome variable to be cone spacing. We will analyze cone spacing as the primary prespecified outcome, but also conduct an analogous analysis of cone density. Cone spacing as well as cone density will be measured longitudinally in regions of interest *selected prior to randomization and surgery* and followed over time. Specifically, as detailed in the flow sheet of examination procedures in the Protocol, we will consider acquiring measurements at the following times:

Baseline 1, within 7 weeks of implant surgery

Baseline 2, within 4 weeks of baseline 1

Six months (plus or minus 7 days)

Twelve months (plus or minus 14 days)

Eighteen months (plus or minus 14 days)

Twenty-four months (plus or minus 14 days)

Thirty months (plus or minus 14 days)

Thirty-six months (plus or minus 14 days)—this measurement is the primary outcome and is required

A minimum of seven regions of interest per eye will ideally be established from the Baseline 1 images. These specific regions will be followed longitudinally. Note that if outcome data were not available at a specific visit due to inability to acquire images from patients, the study could

optionally be continued at the discretion of the DSMC. Such decisions would be made independent (masked to) all outcome data.

The primary hypothesis test uses the 36-month observations.

We use the following notation. The data are hierarchical, with region nested within eye and eye nested within person. Let each region within each eye be labeled k , $k=1, \dots, n_{ij}$, where n_{ij} is the number of regions of interest identified within eye j of person i . We denote the control eye by $j=0$, and the treatment eye by $j=1$. We denote the study time by ℓ , with $\ell=0$ representing baseline, and $\ell=1$ representing the final followup. We let $Y_{ijk\ell mg}$ denote the outcome variable for person i , eye j , region k , time ℓ , repetition m , and grader g . In the case of the baseline visit, $m=1, 2$; for the followup, $m=1$; grader $g=1, 2$ identifies the two graders. We denote the foveal distance of each region of interest as D_{ijk} ; each region of interest is prospectively identified and followed over time, and these distances are therefore constant over time.

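### The Protocol and the SAP define different primary analyses (24- or 30-month rates of spacing and density against a 36-month Z-score change in spacing), and the stated power describes neither the SAP's horizon nor its scale

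*SAP*

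**What the plan says.** **Protocol.**

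- Summary: "The primary efficacy variable is the rate of change in cone spacing and cone density from baseline to 30 months". Section 4.1 agrees on the horizon and gives the method: the comparison runs between treated and "contralateral sham-treated eyes through 30-months using pooled linear regression".
- Section 6.3: "The primary efficacy variable is the rate of change in cone spacing and cone density from baseline to 24 months". Section 2.3 says the study will "explore the effect on cone spacing and cone density over a 24-month period", and 6.4 sets the primary comparison "over the 24-month study period using pooled linear regression".
- Section 4: "All participants will be followed clinically for 30 months". Table 1 nevertheless schedules AOSLO at 36 months.
- Sections 4.1, 4.7 and 11.1 specify three graders.
- Section 6.5 says only that a SAP will be written and approved by the Principal Investigator and the Sponsor.

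**SAP v2.0, 7.5.1.1.** "The primary hypothesis test uses the 36-month observations". Spacing is the outcome for formal testing; density is analysed in parallel and is called strictly secondary in 3.2. The outcome is a Z score. The change from the mean of two baselines is averaged over two graders and over regions, then differenced between eyes to give one value U per person. The hypothesis that U has mean zero is to be tested with a Wilcoxon rank sum test. Mixed models of the longitudinal data (7.5.1.3) are complementary.

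**Power.** SAP 3.1.2 and 3.1.5 plan on 0.084 arcmin over two years. Protocol 6.4 uses the same difference, described as "twice the effect reported per year in preliminary studies". Density power (SAP 3.2) is also at two years.

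**The concern.** The documents differ on four features of the primary analysis: horizon, outcome (a rate in two measures or a change in one), method and number of graders. The Protocol also disagrees with itself on horizon. Someone holding the trial to its Protocol would expect a different primary result from the one the SAP produces, and could not tell from the Protocol which result was prespecified.

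Three smaller defects sit inside the SAP's own primary analysis.

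- The named test compares two samples, but U is one sample of paired differences, so the test cannot be run on U as named.
- SAP 7.5.1.2, and the sentence in 2.3.1 introducing an additional primary measure, say spacing where the surrounding text shows density is meant. Read literally, 7.5.1.2 demotes the tested outcome to secondary.
- The power statement is in arcminutes at two years, while the test uses Z scores at 36 months.

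**Working it through.** **1. The two specifications side by side**

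| Feature | Protocol | SAP v2.0 |
|---|---|---|
| Outcome | spacing and density | spacing (density secondary for testing) |
| Quantity | rate of change | change from mean of two baselines, Z score |
| Horizon | 30 months (Summary, 4.1); 24 months (2.3, 6.3, 6.4) | 36 months |
| Method | pooled linear regression | rank test on one U per person |
| Graders | 3 | 2 |

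**2. The SAP's sample size.** Inputs: difference 0.084, SD 0.11, two-sided alpha 0.05, 80% power, 15% loss (SAP 3.1.1 to 3.1.5). The standardised effect is 0.084/0.11 = 0.764. The normal formula, ((1.96 + 0.842)/0.764)², gives 13.5, so 14. The exact noncentral t gives 16 (power 81.4%), and 17 people give 84.0%. The SAP states 17, and 17/0.85 = 20, as stated. The calculation therefore reproduces to within one person of the exact result, strictly as a two-year arcminute calculation.

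**3. What the 0.11 measures.** Protocol 6.4 calls it a within-region SD, SAP 3.1.3 the SD of a difference between slopes, and SAP 3.1.5 the SD of the difference in two-year change. The reading matters. Taken as the SD of the paired difference, 0.11 gives the Protocol's 10 patients 57.7% power. Taken as a per-region SD averaged over seven independent regions, it gives 98% or more.

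**4. Power at 36 months (assumed inputs).** The documents give no 36-month effect or SD, and none on the Z scale. I take 17 evaluable people and a paired t-test. The effect is either linear (0.084/2 × 3 = 0.126) or unchanged at 0.084. The SD is constant, grows with the square root of time (0.11 × √1.5 = 0.135), or grows linearly (0.11 × 1.5 = 0.165).

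| SD | Power at 0.126 (N for 80%) | Power at 0.084 (N for 80%) |
|---|---|---|
| 0.11 | 99% (9) | 84% (16) |
| 0.135 | 95% (12) | 67% (23) |
| 0.165 | 84% (16) | 51% (33) |

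**5. How often the two analyses disagree.** I simulated 20,000 trials per cell. Each person's between-eye difference is b·t plus independent visit error, at two baselines and every six months to three years. The mean of b is 0.042 arcmin/year, and the two-year change has variance 0.11², of which a share f comes from true slope differences. The Protocol analysis is a per-person least-squares slope with a one-sample t-test, which is one reading of pooled linear regression. The SAP analysis is U at 36 months with a one-sample t-test. Both are in arcminutes. Entries are the percentage of trials with different verdicts at the 5% level.

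| n, slope horizon | f = 0 | 0.25 | 0.5 | 0.75 | 0.9 |
|---|---|---|---|---|---|
| 17, 24 months | 9.4 | 10.4 | 10.3 | 8.7 | 5.8 |
| 17, 30 months | 1.6 | 4.2 | 6.6 | 6.5 | 4.7 |
| 25, 24 months | 1.6 | 2.3 | 2.8 | 2.8 | 2.0 |
| 25, 30 months | 0.1 | 0.5 | 1.4 | 1.8 | 1.6 |

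Here 25 is 30 less 15% (25.5, rounded down). Repeat runs at n = 17 stayed within roughly 5% to 11% (24 months) and about 2% to 7% (30 months). At 24 months most of the disagreement is the SAP test succeeding where the slope fails; at f = 0 and n = 17 this is about 8.9 of the 9.4 points. With half the planned effect (0.021/year, assumed) and n = 17, disagreement ranges from 8.8% to 42.1% (24 months) and 7.6% to 37.6% (30 months), so the table is not a bound.

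**The case against.** The strongest reply is that the SAP is the later and more detailed analysis document, that Protocol 6.5 delegates the analysis to it, and that it is clear on outcome and horizon. It also says openly that power rests on a simplified version of the planned analysis. Most of this stands: taken alone, the SAP leaves no choice of outcome or time point. But delegating the analysis does not redefine the Protocol's primary endpoint, and Protocol 10.3 requires approval by the SMC, IRB and sponsor for changes that affect scientific validity.

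Four stronger readings are tempting, and the documents do not support them.

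- *The trial is underpowered at 36 months.* Not shown. The direction depends on effect growth and on an SD that the documents do not give.
- *The rank sum test throws away the pairing.* The SAP defines one U per person and a null mean of zero, and plans on a paired t-test. There is no second sample to rank, so this is a misnamed one-sample test and a one-word correction.
- *Spacing is really secondary.* The text of SAP 2.3.1, 3.2 and 7.5.1.1 shows that 7.5.1.2 is a labelling slip.
- *The disagreement rates measure damage.* Correlated tests always disagree sometimes, and at 24 months most of the disagreement favours the SAP's test.

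**Conclusion.** The conflict is real, stands in current text and should be fixed. It is a reconciliation problem between a Protocol that is inconsistent about its own endpoint and a SAP that is determinate on outcome and horizon but misnames its test. No available passage says which document prevails; the title pages were not available to check.

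Under linear effect growth and the assumptions above, the choice of document changes the verdict in a minority of trials: roughly 5% to 11% or 2% to 7% with 17 people, and at most about 3% with 25. These figures are conditional on arcminutes, t-tests, independent visit errors and one reading of the Protocol's regression. No size is put on the two-versus-three grader difference. The stated power does not describe the 36-month Z-score test, and whether true power is above or below 80% is undetermined.

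**What to change.** 1. **One primary.** In Protocol Summary, 2.3, 4.1, 6.3 and 6.4, state the SAP's primary: 36-month change in cone spacing, one U per person, density secondary for testing. Replace the two-measure rate and the pooled regression wherever they define the primary. Note in the amendment that the title's reference to rates in both measures no longer describes the tested outcome. Say in 6.5 that the SAP's primary analysis governs.
2. **Timing.** Date the change and make it before any unmasked outcome comparison is used. This matters because SAP 6.2.2 has an unmasked statistician preparing SMC reports that list outcomes. If that point has passed, report the SAP analysis as a deviation from the Protocol and show the Protocol's slope analysis beside it.
3. **Test.** In SAP 7.5.1.1 name the Wilcoxon signed-rank test on U. Keep the mixed model as supporting.
4. **Graders.** Use one count in Protocol 4.1, 4.7 and 11.1, the SAP change-score formula and the imputation steps of SAP 7.6.2.
5. **Labels.** Change spacing to density in SAP 7.5.1.2 and in the additional-primary sentence of 2.3.1, and correct the sentence after it.
6. **Power.** Restate power or detectable effect at 36 months on the test's scale, defining the SD and stating the assumed effect growth.
7. **Flag only, for the sponsor to reconcile.** The 30-month statements in Protocol 4 (follow-up), 5.6 (withdrawal visit) and 6.2 (subgroup), and the 30- and 36-month visit windows (21 days in Table 1, 14 in the SAP).

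The cost is wording, one power calculation and an amendment with the approvals in Protocol 10.3. No visit or image is added, since the 36-month AOSLO is already scheduled. The downside is that more images may be missing, and need imputing, at 36 months than at 24.

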4.2 Inclusion Criteria

1. Participant must be between 18 and 55 years of age.
2. Participant must have a diagnosis of retinitis pigmentosa or Usher syndrome type 2 or 3.
3. Participant must understand and sign the protocol informed consent. If the participant's vision is impaired to the point where he/she cannot read the informed consent document, the document will be read to the participant in its entirety.
4. Best-corrected visual acuity must be no worse than 20/63 (at least 59 letters).
5. Participants must have clear natural lenses.
6. Participants must have less than 6 diopters myopia.
7. Participants must be medically able to undergo ophthalmic surgery for the NT-501 device insertion and be able to undergo all assessments and tests associated with the protocol.

8. Females of childbearing potential (**women with last menses \leq 1 year prior to screening**) must agree to use an effective form of birth control from study onset until they complete the study.
9. Participants must have reproducible baseline AOSLO image montages at 2 baseline imaging sessions with quality suitable to identify a minimum of 7 regions of interest (ROIs) at which reliable cone spacing and/or density measures can be made over the central 5.7 degrees.
10. Participants must have interocular symmetry of disease severity as measured by cone spacing, with a difference of less than 2 standard deviations in average cone spacing z-scores at the selected ROIs between the 2 eyes.
11. Participant's clinical diagnosis must be consistent with retinal degeneration in the set of retinitis pigmentosa (RP) dystrophies characterized by the following features:
 - a) clinical evidence of progressive photoreceptor cell dysfunction and degeneration of the outer retina
 - b) intraretinal 'bone-spicule'-like pigment observed on clinical examination
 - c) peripheral visual field constriction documented on standard testing
 - d) symptomatic night blindness
 - e) reduction of both rod and cone electroretinogram (ERG) responses.

For purposes of this study, individuals diagnosed with Retinitis Pigmentosa or Usher Syndrome Type 2 or Type 3 (without profound deafness or cochlear implants) who meet the inclusion criteria will be considered as potential candidates for this study. A maximum of 4 Usher Syndrome Type 2 or Type 3 participants may be enrolled in this trial.

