3.1.5 Sample size calculation methodology

We used a simplified version of the analysis we plan in order to estimate the power for the more complex analysis. This reduces the analysis to a paired T-test. More specifically, we determined the rate of change over time of the cone spacing in our pilot patients, and computed a pooled standard deviation over all these regions (in untreated persons) from which we derived an expected standard deviation of the difference in the total change in cone spacing after two years of approximately 0.11. Using the standard formula for the sample size of a one-sample T-test

(e.g. Chow et al, 2007, formula 3.1.2), we find we would need a total of 17 individuals per group, or 20 adjusting for loss to follow-up.

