3.2 Secondary outcomes

The sample size was determined with respect to the single prespecified primary outcome variable for hypothesis testing, cone spacing.

For the second primary outcome variable, **cone density**, we calculate the effect size for which our power is 80% as follows (although we will perform hypothesis tests here, this analysis is strictly secondary). We fitted a linear regression (ordinary least squares) to cone density over time in each region of interest in a small subset of patients (Talcott et al, 2011); we estimated the standard deviation of the regression slopes, and used this to estimate the standard deviation in the difference in the change at 2 years. Using this in the sample size formula for a one-sample T-test (Chow et al, 2007) yields an effect size of approximately 5% of the baseline value of cone density over two years. Expressed differently, if the true effect of the implant is to result in 5% more cones relative to baseline than the control eyes, we have 80% power to detect this effect. Assuming our standard deviation estimate is too optimistic, with the true value being 30% higher, we have power to detect a difference of 7% in cone density relative to baseline at 2 years.

For **visual acuity**, we have 80% power to detect a standardized effect size of 1.02 (using the standard formula for a one-sample T-test cited above), considering the outcome to be the change in the difference in acuity between the treatment and control (sham-implant) eyes. Using a standard deviation for the signed visual acuity difference between two eyes at baseline of 0.05 logMAR (e.g. Brown and Yap, 1995) and assuming independence of changes, we would expect greater than 80% power to detect an effect size of 0.1 logMAR in the change in the difference between two eyes. We do not have adequate information at this time regarding the standard deviation of the visual acuity difference between the eyes in our patient population or of the expected correlation between two time points assuming no treatment effect.

For changes in **visual field sensitivity**, **foveal sensitivity**, **outer nuclear layer**, **outer segment thickness**, and **changes in ERG measurements**, we will be able to obtain variance information which will be useful in planning future studies. We will report confidence intervals for estimated effects. Note that the trial will also provide information needed to plan further studies of retinal function and cone spacing/density.

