7.5 Hypothesis Tests

7.5.1 Analysis of primary outcome

We describe an analysis template for continuous outcomes which will be repeated as indicated.

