Z scores will be used as the prespecified outcome variable, based on analysis of normal subjects. Spacing is determined by analysis of images, by two independent graders.

The baseline score for a region of interest for each grader is $(Y_{ijk01g} + Y_{ijk02g})/2$. The change score for each region of interest for grader g is $\Delta_{ijkg} = Y_{ijk\ell 1g} - (Y_{ijk01g} + Y_{ijk02g})/2$. The mean change score (averaging over graders) is $\Delta_{ijk} = (\Delta_{ijk1} + \Delta_{ijk2})/2$. The average change score for each eye is $\Delta_{ij} = (\sum_k \Delta_{ijk})/n_{ij}$. The difference between the treatment and control eyes for person i is $U_i = \Delta_{i1} - \Delta_{i0}$.

Under the null hypothesis, the differences U in change between treatment and control should have mean 0. We test this hypothesis using the Wilcoxon rank sum test.

Additional analyses may be reported. In each case, we will distinguish between such supplementary analyses and the primary analysis.

- The grader-specific difference in change scores, analyzed using Rosner's clustered version of the Wilcoxon rank sum test
- Analyses of covariance, in which the baseline is used as a regressor and the outcome variable is the final value. These models will be at the level of the individual ROI, clustering on eye and person.
- Subset analyses in which the analysis is restricted to regions of interest in which both graders' results are available at all visits. Note that this does not eliminate bias, since missingness of follow-up data occur post-randomization.

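### The SAP names the Wilcoxon rank sum test, a test for two independent samples, for a primary statistic that is one paired difference per person

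*SAP*

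**What the plan says.** SAP 7.5.1.1 averages the change scores over graders and regions of interest within each eye, then subtracts the control eye from the treated eye. This leaves one number per person, U_i = Δ_i1 − Δ_i0. The null is put on that number: "Under the null hypothesis, the differences U in change between treatment and control should have mean 0". The next sentence is "We test this hypothesis using the Wilcoxon rank sum test".

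The planning sections treat the data as paired. SAP 3.1.5 says of its simplified planning analysis, "This reduces the analysis to a paired T-test", and obtains its number "Using the standard formula for the sample size of a one-sample T-test". Protocol 6.4 describes its calculation as "using a paired-subjects t-test as a basis for power calculations". For visual acuity, SAP 3.2 works with one between-eye quantity per person, "considering the outcome to be the change in the difference in acuity between the treatment and control (sham-implant) eyes".

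SAP 7.5.1 introduces the section as reusable: "We describe an analysis template for continuous outcomes which will be repeated as indicated". SAP 7.5.1.2 and the subsections of 7.5.2 on acuity, visual field, foveal sensitivity, outer nuclear layer, outer segment and ERG refer back to it, directly or through the acuity subsection.

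Neither document mentions a signed-rank test. The only other rank test is a clustered rank sum test, listed in 7.5.1.1 as an optional grader-specific analysis.

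**The concern.** Rank sum needs two independent groups of observations. U_i is one sample, so the named test cannot be applied to the quantity defined just before it. Whoever runs the analysis must either change the test (signed-rank on U_i) or change the data (rank sum on treated-eye changes against sham-eye changes). The second choice treats two eyes of one person as unrelated.

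These choices give different p-values for the one test that carries the trial's two-sided 0.05. In R, the software named in SAP 7.6.1, they differ only in the call: `wilcox.test` with one vector runs signed-rank, and with two vectors and no paired option it runs rank sum. If the SAP is not corrected before analysis, there is room to dispute which test was prespecified. Because the section is a template, the wrong name may also carry over to the secondary outcomes.

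**Working it through.** **Inputs from the documents.** Two-sided alpha 0.05 (SAP 3.1.1). Effect 0.084 arcminutes over two years and 80% power (SAP 3.1.2). SD of the between-eye difference in two-year change 0.11 (SAP 3.1.5). Loss to follow-up 15% (SAP 3.1.4). Sample size 17, or 20 after loss (SAP 3.1.5); SAP 3.3 also randomizes 20.

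**Assumed.** The correlation ρ between the two eyes' changes is not given, so a range is shown. Data are taken as normal on the two-year arcminute scale, whereas the primary test uses 36-month z-scores.

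**1. The plan's own figure.** Standardized effect = 0.084 / 0.11 = 0.764. A one-sample t-test (noncentral t) has 81.4% power at n = 16 and 84.0% at n = 17. The stated 17 is one above the minimum and is reproduced to within rounding. Then 17 / (1 − 0.15) = 20. The sizing is that of a one-sample test on U.

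**2. Signed-rank on U_i, same inputs.** Exact critical values: reject at min(W+, W−) ≤ 34 for n = 17 (attained level 4.48%) or ≤ 52 for n = 20 (4.84%). Simulated power is 78% at n = 16, 81% at n = 17 and 88% at n = 20. The planned 17 and 20 stand under this test.

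**3. Rank sum on the two sets of eyes.** Exact critical values: reject at Mann-Whitney statistic ≤ 87 for n = 17 (4.87%) or ≤ 127 for n = 20 (4.91%). These levels hold only for independent samples. Since Var(U) = 2σ²(1 − ρ), holding SD(U) at 0.11 gives a per-eye SD of σ = 0.11 / √(2(1 − ρ)). Results from at least 40,000 simulated trials per cell:

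| ρ (assumed) | Type I, n = 17 | Type I, n = 20 | Power, n = 17 | Power, n = 20 |
|---|---|---|---|---|
| −0.3 | 8.0% | 8.1% | – | – |
| 0 | 5.0% | 4.9% | 84% | 90% |
| 0.3 | 2.2% | 2.2% | 73% | 81% |
| 0.5 | 0.8% | 0.8% | 57% | 67% |
| 0.7 | 0.2% | 0.2% | 31% | 39% |

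Over the same range signed-rank keeps its level and its 81% or 88% power. On this scaling rank sum is the weaker test once ρ exceeds about 0.1. Its power falls below 80% at ρ of about 0.15 for n = 17 and just above 0.3 for n = 20.

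**4. The other reading of 0.11.** If 0.11 was built up from single-eye variation assuming independent eyes, the per-eye SD is 0.11 / √2 = 0.078 whatever ρ is. Rank sum power at n = 17 is then 84%, 88%, 91% and 95% for ρ = 0, 0.3, 0.5 and 0.7. At positive correlation only the gain from pairing is lost. The type I errors in the table do not depend on this choice.

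**The case against.** The strongest reply is that this is a slip in a name. The SAP defines U_i, puts the null on U_i and says that this hypothesis is tested, so the object of the test is fixed and only its label is wrong. Every figure in the table belongs to the less natural reading. That is right, and it limits the severity. It does not remove the error: rank sum is named twice in 7.5.1.1, no sentence corrects it, and a SAP should not leave its primary test to inference.

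The power loss also depends on scaling and size. SAP 3.1.3 calls 0.11 the SD of a difference in slopes, SAP 3.1.5 derives it from an SD pooled over regions in untreated people, and Protocol 6.4 calls it a within-region SD. The independence reading is therefore open, and under it rank sum is adequately powered. At the roughly 30 participants in the Protocol's study design, even the less favourable scaling gives rank sum power of about 95%, 88% and 65% at ρ = 0.3, 0.5 and 0.7. These points stand, so a loss below 80% is possible, not established.

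Support for positive correlation is indirect. The Protocol 4.2 criterion, "Participants must have interocular symmetry of disease severity as measured by cone spacing", concerns baseline level, not change over 36 months. It makes positive correlation plausible and gives no value. The documents give no reason to expect a negative one, so the inflated 8% is only a boundary case.

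Carry-over to 7.5.2 is possible but not certain, since the acuity subsection speaks of modelling the difference and the ERG subsection uses several time points.

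Two further matters are separate and are not cured by renaming the test. The Protocol gives pooled linear regression as the primary comparison, and SAP 7.6.2 makes a multiply imputed result primary without a rule for combining a rank test across imputations.

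**Conclusion.** The concern holds. The primary test as named does not fit the statistic and null that the SAP defines for it, and nothing in either document puts this right. Signed-rank is the natural rank-based reading, but it is an inference.

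If signed-rank is run on U_i, the planned size, power and error rate are intact and only the text is wrong. If rank sum is run on the eyes, the test is about nominal at zero correlation, conservative at positive correlation and liberal at negative correlation. Its power then ranges from adequate to poor, depending on a correlation, a scaling of 0.11 and a sample size that the documents leave open. This should be fixed before analysis; it does not undermine the design or the data.

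**What to change.** In SAP 7.5.1.1, replace the rank sum test with the Wilcoxon signed-rank test of U_i. State the null as U distributed symmetrically about 0, because signed-rank is not in general a test of a mean. State that the same test applies wherever 7.5.2 uses the template on between-eye differences. If the optional grader-specific differences are analysed, use a clustered signed-rank test so that the supplementary analysis matches the primary one.

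The cost is SAP wording. The data, the software and the planned 17 or 20 people do not change.
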